6.2 Measurements and Evaluations

6.2.1 Screening Period (Up to 14 days prior to Treatment Visit 1)

Before the initiation of screening assessments, the subject/guardian must be given a complete explanation of the purpose and evaluations of the study. Subsequently and depending on the age of the subject, the subject/guardian must sign and receive a copy of an informed consent form (ICF) ([Section 9.3](#)), an IRB-required assent form (subjects 10 years or older), and an authorization for use and disclosure of protected health information ([Section 9.3](#)) that was approved by the IRB. Once consent and assent are obtained, the Screening Period assessments will be performed. Subjects will be screened within 14 days prior to or on Treatment Visit 1 of the study. Following consent and assent, review and recording of any

medical history will take place, and the following evaluations will be performed and recorded in eCRF:

1. Demographics (date of birth, sex, ethnic origin)
2. Height and weight
3. Prior relevant medical history
 - All past relevant illnesses with in the past 5 years.
 - All drugs used (including non-prescription and herbal [complementary medicine] products) within 14 days prior to screening procedures. Any anti-microbial, anti-viral, steroidal or topical drugs received within 30 days prior to Day 1.
 - Any non-pharmacologic treatments (e.g., ice packs, heat packs, warm soaks, etc.) administered in the 72 hours prior to the application of the Study drug.
4. Common wart history (duration and previous treatments). If treated with cantharidin, confirm date of last treatment. Warts must be present for at least 4 weeks prior to screening.
5. Limited physical examination.

6.2.2 Safety Evaluation Period (Treatment Visit 1)

Screening and Treatment Visit 1 may occur on the same day. The following evaluations will be performed and recorded on the source and in eCRF:

1. Confirmation that the inclusion/exclusion criteria are met.
2. Dermatologic exam: Wart count (Cohort 1) and location (head/neck, chest/abdomen, back/buttocks, groin, and upper/lower extremities) and measurement of each wart size (diameter, height) and location. Presence of any confounding dermatologic diseases such as atopic dermatitis. Fitzpatrick skin type.
3. Medical history to assess any changes since screening (as described in Section 6.2.1).
4. Review and recording of any concomitant medications and non-pharmacologic treatments or procedures in the last 30 Days prior to enrollment.
5. Vital signs (heart rate and temperature).
6. Limited physical examination.
7. Urine pregnancy test for females of child-bearing potential, defined as capable of menstruating, to determine protocol eligibility.
8. ERT assessment (LSRs, AEs, Concomitant medications [ConMeds])-prior to treatment.
9. Photographs taken before application of the Study drug if applicable.
10. Paring of warts (Cohort 2), if applicable
11. Application of Study drug and occlusive tape.
12. Subjects will be given take-home instructions describing potential local skin reactions and what they might expect throughout the course of the study, as well as

recommendations for wound care, when it is important to call their doctor and instructions for who to contact in an emergency.

13. A local skin reaction guide for subjects with specific photos identifying the various skin reactions and examples of intensity will be reviewed at the clinic with the subject/guardian by the research team. During the ERT phone call, should a subject report experiencing excessive blistering, ulceration, edema, pain or another adverse event needing physician assessment, they will be scheduled for an “unscheduled” study visit and safety evaluation as soon as possible.
14. Review and record any AEs which include local skin reactions and any concomitant medications.
15. Removal of occlusive tape and Study drug: At 24 hours (+/- 8 hours) after drug application, subjects are instructed to wet the treated area with warm water and then carefully and slowly remove the occlusive tape from each wart, pulling the tape back over itself in a low and slow manner, trying not to unroof any intact blisters. Treated warts should be gently washed with soap and warm water after the tape is removed. The occlusive tape and Study drug may be gently removed from individual warts prior to 24 hours of application in the event of significant blistering, significant pain or treatment emergent AEs. The occlusive tape and Study drug should not be removed from any remaining unproblematic warts until the 24-hour time point is reached. Washing of intact blisters should be gentle and without use of a washcloth. Washing and removal of occlusive tape in a bath or shower is encouraged. Photos should be taken by the subject or guardian after the tape and Study drug are removed.
16. Post treatment ERT phone assessments: At 24-hours and 7 days after treatment, the research team will conduct an ERT assessment over the phone. The ERT includes questions related to removal of the occlusive tape and study drug, if applicable, and records the intensity of any local skin reactions, adverse events and concomitant medications (ConMeds). The subject and/or guardian will have time to ask questions and review any concerns. In the event any adverse events present a safety concern, an “Unscheduled” clinic visit will be made, and the subject assessed accordingly.
17. Occlusive tape and Study drug must be removed prior to the call.
18. Subjects participating in the photo portion of the study will take photos of all lesions every 24 hours for 5 days (Cohort 1) after each treatment up to Day 84 EOS. Cohort 2 will only obtain photos at 24 hours after each treatment and through the Day 147 Follow-up visit. Subjects will either text or e-mail the photos to the research team or bring them to the next Treatment Visit to upload and store.

6.2.3 Safety and Efficacy Evaluation Period: (Treatment Visits 2, 3 and 4)

1. Review and recording of any concomitant medications and non-pharmacologic treatments/procedures since previous visit.
2. Review and recording of any AEs (before and after Study drug application).
3. Vital signs (heart rate and temperature) before Study drug application.
4. Dermatologic exam: (as described in Section 6.2.1) Wart count (Cohort 1), measurement and location (head/neck, chest/abdomen, back/buttocks, groin, and

- upper/lower extremities) of all warts. Measurement of diameter and height. Presence of any confounding dermatologic diseases such as atopic dermatitis.
5. Paring of warts (Cohort 2, if applicable)
 6. ERT assessment (LSRs, AEs, ConMeds)-prior to treatment.
 7. Urine pregnancy test for females of child-bearing potential to confirm continued protocol eligibility before application of study drug.
 8. Photographs taken before application of the Study drug (if applicable). Upload of subject obtained photos if applicable.
 9. Administration of study drug to all warts including those warts that may be newly developed. If any new warts are not treatable, this will be documented by the team member who is applying the treatment.
 10. Subjects will be given take-home instructions describing the potential local skin reactions and what to expect over the next 24 hours to several months.
 11. Removal of occlusive tape and Study drug. (See Section 6.2.2 for details)
 12. Post treatment ERT phone calls: (See Section 6.2.2 for details) safety evaluations will be conducted by the research team via phone calls at 24 hours and 7 days after every treatment application (ERT). The phone call will review questions related to removal of occlusive tape, Study drug, and review and documentation of local skin reactions, adverse events and con-meds since the prior visit or call. If participating, a reminder to take photos of the treated areas and save or send the photos via text or e-mail to the research team will also be reviewed. The subject and/or guardian will have time to ask questions and review any concerns. In the event any adverse events present a safety concern, an “Unscheduled” clinic visit will be made, and the subject assessed accordingly.
 13. In Cohort 1, subjects that achieve complete clearance prior to Treatment Visit 4, ERT phone calls will be conducted at the required 2-week treatment intervals to assess the status of any AE’s or skin reactions since the last visit and confirm there has been no recurrence in treated warts or new warts have developed. Subjects that report recurrence of, or presence of new warts, will be scheduled for a Treatment Visit per protocol. *Sites should consider calling the subject a few days prior to the 2-week interval (e.g., 11 or 12 days) to ensure adequate time for scheduling assessment and treatment if needed.*
 14. In Cohort 2, subjects that achieve complete clearance prior to Treatment Visit 4 will be required to return for each Treatment Visit until EOT as well as Follow-up Visits on Day 105, 126 and 147. The status of any AE’s or skin reactions or any recurrence in treated warts or new warts will be assessed per protocol at each phone call and in-person visit.
 15. Photos taken by subject (per protocol Cohort 1 and 2)

6.2.4 Unscheduled Visit:

May take place at any time, as needed, to evaluate the subjects for safety reasons or for those subjects unable to be treated due to an ongoing LSR. For those subjects evaluated at their

scheduled Treatment Visit as exhibiting untreatable warts, no treatment will be administered, and an “Unscheduled” treatment form will be completed. The following information should be obtained:

1. Reason treatment was not administered.
2. Dermatologic exam.
3. ERT, including LSR, wart count (Cohort 1) and location of all warts.
4. Photos (if applicable).

6.2.5 End of Study Visit (Cohort 1: Day 84) and End of Treatment Visit (Cohort 2: Day 84)

Subjects will return to the clinical site for:

1. Review and recording of any concomitant medications and non-pharmacologic treatments/procedures since previous visit.
2. Review and recording of any AEs.
3. Vital signs (heart rate and temperature) obtained at the beginning of visit.
4. Limited physical examination.
5. Any new warts counted (Cohort 1), measured and documented per protocol.
6. Dermatologic exam, ERT assessment (LSRs, AEs, ConMeds)
7. Provider EOS/EOT Treatment Questionnaire
8. Urine pregnancy test for females of childbearing potential.
9. Photographs taken by the research team/Upload of subject photos if applicable.

6.2.6 Follow-up Visits Cohort 2 (day 105, Day 126, and Day 147)

1. In person: Vital signs,
2. Measurement and location of all warts.
3. Photos (if applicable).
4. Dermatological exam and ERT.
5. Any new warts should be measured and documented per protocol.

7 PROCEDURES FOR HANDLING ADVERSE EVENTS AND SERIOUS ADVERSE EVENTS

7.1 Definition of an Adverse Event

The following definition of *adverse event* (AE) will be used for this study:

Adverse event means any untoward medical occurrence associated with the use of a drug in humans, whether or not considered drug related.

An AE can be any unfavorable and unintended sign, symptom, or disease (new or exacerbated) temporally associated with the use of the investigational product, regardless of whether it is considered to be related to the investigational product.

The following are examples of AEs:

- Exacerbation of a chronic or intermittent pre-existing condition, including an increase in frequency or intensity of the condition
- New conditions detected or diagnosed after investigational product administration, even if they were present before the start of the study
- Signs, symptoms, or the clinical sequelae of a suspected interaction with another medical product
- Local skin reactions (erythema, scaling/flaking/dryness, edema/swelling, small blisters, hyper- and hypopigmentation, scabbing/crusting, erosion/ulcerations, scarring, ring warts)
- Development of individual blisters that are greater than 25mm in diameter (the diameter of a quarter). (An aggregated blister composed of a number of smaller blisters is not considered a severe blister)
- Blistering distal to the treatment site
- Scarring-independent of any pigmentary changes; include depressed (atrophic) and elevated (hypertrophic)
- Secondary infection

The following are not examples of AEs:

- Medical procedures (The medical condition that led to the procedure as the AE should be reported.)
- Situations that are unwanted by the subject but in which an untoward medical occurrence did not occur, for example social inconvenience after admission to a hospital
- Anticipated day-to-day fluctuations of a preexisting disease or condition (present or detected before enrollment) that does not worsen overall

- Expected progression of the disease being studied, including signs or symptoms of the disease, unless progression is more severe than expected for the subject's condition.

AEs may include pre-treatment or post-treatment events that occur as a result of protocol-mandated procedures (e.g., invasive procedures, modification of the subject's previous therapeutic regimen). AEs should be captured even if they occur during periods without drug treatment or post-treatment periods. AE collection begins once the subject has signed informed consent and will continue until the EOS visit has been completed.

The investigator is responsible for performing periodic and special assessments for AEs. The investigator and study personnel will note all AEs mentioned by the subject starting from the day the informed consent is signed until the end of study visit (EOS; Day 84). All clinical complaints volunteered by or elicited from the subject or parent/guardian during the study will be recorded on the appropriate page of the source and eCRF for the study period indicated. The subject will receive appropriate treatment and medical supervision for any AE that occurs.

All unresolved AEs will be followed until the condition resolves and/or stabilize, the subject is lost to follow-up or 30-days after the end of study (EOS visit or up to 30 days after the EOS visit, whichever comes first.) All AEs will be summarized in the annual report or more frequently if requested by the regulatory agency. SAEs require special reporting in addition to documentation in the eCRF as described in Section 7.3.

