It can sometimes be challenging to determine if a wart is completely clear after treatment due to ongoing local skin reactions. At any visit where the investigator is unable to evaluate or treat some warts due to ongoing local skin reactions, an "Unscheduled" Visit should be documented. The timing of the next visit will be determined by the resolution of the local skin reaction. A Treatment Visit should be documented at every visit where Study drug is applied. Treatment should only take place at a visit when all warts are evaluable (i.e., not obscured by an ongoing LSR) and all warts that are not completely clear, should undergo treatment with Study drug. No partial treatment of warts is permitted.

For Cohort 2, Study drug is to be applied to the wart site on any Treatment Visit where a new clinical assessment of complete clearance is made for that wart (*e.g., if a patient returns for Treatment Visit 2 and is clinically assessed to have no visible evidence of remaining wart, then Study drug is to be applied to this wart site at Treatment Visit 2. However, if the patient remains completely clear at that wart site when returning for Treatment Visit 3, then no Study drug would be applied at Treatment Visit 3.*) Should it become clear that the subject will be unable to complete the EOS visit within the allowed window of Day 84 (- 0/+ 8) days, the subject should be brought in for their EOS visit as soon as they are able. This will be documented as a protocol deviation.

In instances where the clinician can adequately assess the treatment sites but is uncertain if residual wart is remaining, treatment should be applied, and the subject should return for evaluation per protocol. Treatment visits and assessments are to take place in order (e.g., Treatment 1, Treatment 2, Treatment 3 and Treatment 4). Subjects that receive fewer than 4 treatments within the 63-day (Cohort 1) or 75-day (Cohort 2) treatment period, due to the duration of post-treatment local skin reactions, will not be considered a protocol deviation. No treatment should be administered after the 63-day treatment period in Cohort 1 or the 75-day treatment period in Cohort 2 without Sponsor's approval.

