assessments with the research team member. Should a subject report experiencing excessive blistering, ulceration, edema, pain or another adverse event needing physician assessment, they will be scheduled for an “Unscheduled” study visit and safety evaluation as soon as possible.

- Medical history, vital signs, and physical examinations:
 - Medical history, wart history, Fitzpatrick Skin Type and limited physical exams will be collected for each subject. A limited physical examination will be completed before the first treatment and at the EOS visit. Vital signs (temperature and heart rate) will be obtained before the treatment is applied at each visit and at the start of the Day 84 (EOS) Visit. Additional physical examinations will be performed when clinically warranted (e.g., subject reports symptoms classified as an AE requiring further evaluation).
- Limited physical examinations will be performed by a qualified medical practitioner at screening and at EOS visits. Height and weight will be recorded at the screening visit and at the EOS Visit. Unscheduled physical examinations will be performed when clinically warranted (e.g., if a subject reports signs or symptoms requiring further evaluation).
- Vital signs (e.g., heart rate and temperature) will be obtained at all Treatment Visits prior to treatment. A final assessment of vital signs will be obtained at the EOS Visit.
- If the subject discontinues the study prematurely (after the first treatment) for any reason, attempts will be made to encourage the subject/guardian to complete the EOS assessments.
- Subjects will be monitored for signs and symptoms of AEs throughout the study. All AEs (including LSRs) will be reported on the source and in the electronic case report form (eCRF), including seriousness, severity, action taken, and relationship to the Study drug. If AEs should occur, the first concern will be the safety of the subject.

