8 STUDY OR SITE TERMINATION AND SUBJECT DISCONTINUATION

8.1 Subject Discontinuation

Subjects are encouraged to complete the study; however, they may voluntarily withdraw at any time. The investigator will provide a written explanation of the reason for discontinuation in a source document and this information will also be recorded on the appropriate eCRF page. If a subject withdraws before completion, every effort should be made to complete the Day 84 assessments scheduled during the End of Study visit.

A subject may be removed from the study for the reasons described in Section 8.1.1 through Section 8.1.5.

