9.2.3 Efficacy Analysis

Efficacy analysis using the ITT population will be considered the primary analysis. Analysis carried out on the per-protocol population will be considered secondary in nature.

The primary endpoint of proportion of subjects exhibiting clearance of all treatable warts (baseline and new) at the EOS/EOT Visit (Day 84 for Cohort 1 and Cohort 2) will be summarized using counts and percentages. The analysis will be separate for Cohort 1 and Cohort 2. Other binary endpoints will be analyzed with this method. Continuous endpoints will be summarized using summary statistics (n, mean, standard deviations, median, minimum, maximum). Further details of analysis of other endpoints will be described in the statistical analysis plan.

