9.2.7 Handling of Missing data

Clearance of all treatable warts is to be assessed at each Treatment Visit as well as unscheduled visits over the duration of the study. The assessment done at the EOS Visit (Day 84) will be considered to be the primary efficacy endpoint.

Subjects who do not have an assessment of complete clearance of all treatable warts at the EOS Visit (Day 84) will be considered to have missing data for the primary endpoint. The primary method to handle missing data will be to assign all subjects with missing complete clearance data as not having achieved complete clearance.

The procedures for handling missing data for other study endpoints will be described in the statistical analysis plan.

9.3 Informed Consent/Assent and Authorization for Use and Disclosure of Protected Health Information

Written assent and informed consent and authorization of use and disclosure of protected health information must be obtained from each subject (or the subject's legally acceptable representative) before performing any study-specific screening/baseline period evaluations. One copy of the signed informed consent form (and IRB-required assent form) and authorization for use and disclosure of protected health information form will be given to the subject, and the investigator will retain the original. The informed consent/assent form and authorization for use and disclosure of protected health information, which is prepared by the investigator or the site, must have been reviewed and approved by the sponsor, the study monitor, and the investigator's IRB and privacy board (if separate from the IRB) before the initiation of the study. The informed consent form must contain the 20 elements of informed

consent described in International Council for Harmonisation E6, Section 4.8. The authorization for use and disclosure of protected health information must contain the elements required by Title 45 of the Code of Federal Regulations, Section 164.508(b), and any local regulations for valid authorizations.

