It can sometimes be challenging to determine if a wart is completely clear after treatment due to ongoing local skin reactions. At any visit where the investigator is unable to evaluate or treat some warts due to ongoing local skin reactions, an “Unscheduled” Visit should be documented. The timing of the next visit will be determined by the resolution of the local skin reaction. A Treatment Visit should be documented at every visit where Study drug is applied. Treatment should only take place at a visit when all warts are evaluable (i.e., not obscured by an ongoing LSR) and all warts that are not completely clear, should undergo treatment with Study drug. No partial treatment of warts is permitted.

For Cohort 2, study drug is to be applied to the wart site on any Treatment Visit where a new clinical assessment of complete clearance is made for that wart (e.g., if a patient returns for Treatment Visit 2 and is clinically assessed to have no visible evidence of a remaining wart, then Study drug is still to be applied to this wart site at Treatment Visit 2. However, if the patient remains completely clear at that wart site when returning for a subsequent visit such as Treatment Visit 3, then no Study drug would be applied at Treatment Visit 3.) Should it become clear that the subject will be unable to complete the EOT visit within the allowed window of Day 84 (+/- 8) days, the subject should be brought in for their EOT visit as soon as they are able. This will be documented as a protocol deviation.

In instances where the clinician can adequately assess the treatment sites but is uncertain if a residual wart is remaining, treatment should be applied, and the subject should return for evaluation per protocol. Treatment visits and assessments are to take place in order (e.g., Treatment 1, Treatment 2, Treatment 3 and Treatment 4). Subjects that receive fewer than 4 treatments within the 75-day (Cohort 2) treatment period, due to the duration of post-treatment local skin reactions, will not be considered a protocol deviation. No treatment should be administered after the 75-day treatment period in Cohort 2 without Sponsor’s approval.

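### Protocol 7.1 ends adverse event noting at Day 84 for every subject, but Cohort 2 adverse events are scheduled through Day 147, and the cut-offs that depend on EOS give no day

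*Protocol*

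**What the plan says.** **AE noting.** Protocol 7.1 runs noting from consent "until the end of study visit (EOS; Day 84" and names no cohort. The same section has a sentence that runs AE collection to the completed EOS visit without giving a day. It also says that "AEs should be captured even if they occur during periods without drug treatment or post-treatment periods".

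**Cohort 2 schedule.** In Protocol Table 2 the Adverse Events row is marked in the follow-up column (Days 105, 126 and 147). Footnote c places the final in-person safety assessment at Day 147 and calls that visit EOS.

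**The label EOS in Cohort 2 text.** A paragraph of Protocol 4.1 that opens with a Cohort 2 rule speaks of a subject "unable to complete the EOS visit within the allowed window of Day 84 (- 0/+ 8) days". Later in 4.1, and in Table 2 footnotes c, e, j and p, EOS is Day 147.

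**EOS as Day 84 with no cohort named.** Examples are Protocol 4.3.1 ("at the start of the Day 84 (EOS) Visit"), 8.1 ("every effort should be made to complete the Day 84 assessments scheduled during the End of Study visit") and 9.2.7 ("The assessment done at the EOS Visit (Day 84) will be considered to be the primary efficacy endpoint"). Protocol 9.2.3 avoids the problem with a joint label: "at the EOS/EOT Visit (Day 84 for Cohort 1 and Cohort 2".

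**Rules that depend on EOS.** Protocol 9.2.4 and SAP 10.2 keep AEs with onset after the EOS visit out of the summary tables but leave them in the listings. Protocol 7.1 and 7.8 follow unresolved AEs for up to 30 days after EOS. None of these rules gives a day.

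**Cohort 2 SAP.** SAP Section 3 repeats the 4.1 sentence with the label changed: "unable to complete the EOT visit within the allowed window of Day 84 (+/- 8) days". SAP 7.1 sets study completion at Day 147.

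**The concern.** Safety and tolerability form a primary objective for Cohort 2, and local skin reactions are counted as AEs. Section 7.1 is the protocol's instruction to sites on how long to note AEs. For Cohort 2 it gives a stopping day that Table 2 contradicts, so a site cannot satisfy both.

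The loss would happen at the site. An AE that is recorded but falls after a table cut-off still appears in the listings. An AE that was never noted appears nowhere and cannot be recovered at analysis. The Cohort 2 follow-up visits exist to look at durability and continuing local skin responses (Table 2 footnote p), so this is a period the protocol means to observe.

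**Working it through.** The plan states no figure to reproduce. The check compares passages and then counts days.

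**1. Is the conflict real for Cohort 2?** Table 2 has 16 visit columns. The Adverse Events row is blank at Screening and marked in the other 15, including EOT, follow-up and Unscheduled. AE assessment is therefore scheduled after Day 84, while 7.1 stops noting at Day 84. The visit list in Protocol 6.2.6 has no separate AE line, unlike 6.2.5. At follow-up AEs are reached through the ERT, which 6.2.5 describes as covering AEs. So 6.2.6 does little to correct a reader of 7.1.

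**2. Does EOS have one day in Cohort 2?** No. It is Day 84 in one paragraph of 4.1, and Day 147 later in 4.1 and in four Table 2 footnotes.

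**3. How much time is at stake?** Inputs: EOT at Day 84 with window -0/+8; last follow-up at Day 147 with window +/-4 (Protocol 4.1, Table 2).

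Gap = last follow-up day − EOT day; share = gap ÷ last follow-up day.

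| Case | EOT day | Last follow-up day | Gap (days) | Share |
|---|---|---|---|---|
| Nominal | 84 | 147 | 147 − 84 = 63 | 63/147 = 42.9% |
| Shortest | 84 + 8 = 92 | 147 − 4 = 143 | 143 − 92 = 51 | 51/143 = 35.7% |
| Longest | 84 | 147 + 4 = 151 | 151 − 84 = 67 | 67/151 = 44.4% |

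SAP Section 3 gives the EOT window as +/-8 rather than -0/+8. On that window the earliest EOT visit is Day 76 and the longest gap is 151 − 76 = 75 days. I use the protocol's window because 7.1 is a protocol instruction.

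**4. Observation after the last treatment (nominal visit days).**
- Last treatment at the planned Day 63 (SAP Section 8): 84 − 63 = 21 days under 7.1 as worded, against 147 − 63 = 84.
- Last treatment at Day 75, the last day allowed without sponsor approval: 84 − 75 = 9 days, against 147 − 75 = 72.

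**5. Follow-up of unresolved AEs.** The 30-day limit falls at 84 + 30 = Day 114 or 147 + 30 = Day 177, depending on which EOS is meant.

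**The case against.** The best reply is that the Day 84 wording is left over from Cohort 1 and that the documents otherwise point to Day 147. Much of this stands. The adjacent sentence in 7.1 runs collection to the completed EOS visit, Table 2 schedules the assessments, and serious AE reporting in 7.7 has no Day 84 end. A site that follows the schedule will collect late AEs. The unqualified Day 84 labels in 4.3.1, 8.1 and 9.2.7 are correct for Cohort 1; only the 4.1 sentence sits in Cohort 2 text, and the SAP has already relabelled it.

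The reply does not remove the error. The adjacent sentence in 7.1 relies on the term that is in doubt, and the sentence that does give a day gives the wrong one for Cohort 2.

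Four stronger readings are tempting but not supported:

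- **That the plan excludes follow-up AEs from the tables.** The Cohort 2 SAP calls Day 84 EOT, sets completion at Day 147, and applies visit windows running to Day 157 to by-visit safety data (SAP Sections 8 and 10). A Day 84 table cut-off is unlikely. SAP 10.2 still gives no day, and SAP 10.6 collects height and weight at EOS where the Table 2 grid marks EOT, so the SAP's usage is not fully settled.
- **That Protocol 6.1 creates a third EOS, at Day 105.** Its sentence placing EOS 42 days after Treatment Visit 4 follows text on 14-day scheduling. Table 1 footnote b targets the Cohort 1 EOS six weeks after the fourth treatment: three 14-day intervals give 42, and 42 + 42 = 84. It is Cohort 1 text.
- **That a Cohort 2 subject who misses Day 147 loses Per Protocol status.** Protocol 9.2.2 says EOS, but SAP Section 6 uses EOT for the same criterion.
- **That 6.2.3 item 14 requires AE assessment through Day 147 for all of Cohort 2.** It covers subjects who clear before Treatment Visit 4. Table 2 carries the general requirement.

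**Conclusion.** The point holds as an error in a stated site rule, together with undated cut-offs, and should be corrected. For Cohort 2, 7.1 ends AE noting at a day that Table 2 contradicts, and the table cut-off and the 30-day follow-up rest on a label with two meanings.

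If a site applied 7.1 literally, 63 of 147 nominal days would go unrecorded (51 to 67 days with the protocol's windows), from listings and tables alike. If EOS is read as Day 147 throughout, nothing is lost. The figures assume that noting stops at the Day 84 visit and that the subject attends through Day 147. They measure time, not events: the documents give no AE rate after Day 84, and local skin reactions may cluster soon after treatment. The primary clearance rate is not affected, because the Cohort 2 endpoint is fixed at the Day 84 EOT visit in Protocol 4.3 and the SAP.

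**What to change.** 1. In Protocol 7.1, 7.8 and 9.2.4 and SAP 10.2, state that EOS is Day 84 for Cohort 1 and Day 147 for Cohort 2, with Day 84 being EOT in Cohort 2. Tie AE noting, the cut-off for treatment-emergent AE tables and the 30-day follow-up of unresolved AEs to that day.
2. In the Cohort 2 paragraph of Protocol 4.1, relabel the Day 84 visit EOT, as SAP Section 3 already does.
3. In Protocol 9.2.2 and 9.2.7, and in the matching Per Protocol sentence of the synopsis, use the joint label EOS/EOT Visit (Day 84), following 9.2.3. Without this step, defining EOS as Day 147 would move the Cohort 2 missing-data and Per Protocol rules off Day 84.
4. For tidiness, the unqualified Day 84 labels in 4.3.1 and 8.1 could take the same joint label.

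The cost is wording in six protocol sections (4.1, 7.1, 7.8, 9.2.2, 9.2.4, 9.2.7), one synopsis sentence and one SAP section, plus the optional labels in step 4. No new data are needed, because Table 2 already schedules AE assessment at the follow-up visits. Sites should be told of the 7.1 change directly, since AEs that were not noted cannot be recovered.
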